9.4. End-of-Study Definition

A clinical trial is considered completed when the last participant's last study visit has occurred. A participant is considered to have completed the study if they have completed all study visits including the 12-Month Visit. Upon end of study, subjects will be followed per standard of care.

10. Study Methods

10.1. Data Collection

The data collection schedules are shown in Tables 10.1-1.

10.2. *Study Candidate Screening*

All interested subjects will undergo screening during which their eligibility for the Registry will be determined.

10.2.1. Informed Consent

Written Informed Consent must be obtained from all potential study candidates before any study-specific tests or procedures are performed.

- The context of the study must be fully explained to the patient and patients must be given an opportunity to ask questions and have those questions answered to their satisfaction.
- Study personnel should explain to each potential participant that even if he or she agrees to participate in the study and signs an informed consent form, further testing might demonstrate that he or she is not eligible for the study.
- Written informed consent must be recorded appropriately by means of the subject's dated signature.

- The consent process must be documented in the subject's medical chart.

10.2.2. *Screening Period*

Subjects' eligibility for the study will be assessed based on study Inclusion and Exclusion criteria listed in Sections 8.2 and 8.3, respectively. Any subjects that do not meet the criteria defined in the local Directions for Use (DFU) will be withdrawn.

10.3. *Baseline Visit (up to 30 days following Informed Consent)*

At the Baseline Visit, subjects will return to the clinic to complete assessments. Any reportable adverse events or changes in opioid pain medications since the last study visit will be collected.

- [REDACTED]
- [REDACTED]
- [REDACTED]
- [REDACTED]
- [REDACTED]
- [REDACTED]
- [REDACTED]
- [REDACTED]
- [REDACTED]
- [REDACTED]

Subjects that meet all criteria will be scheduled for the radiofrequency (RF) ablation procedure. If a subject is not a good candidate and/or fails to meet all the criteria defined in the local DFU, they will be withdrawn from the study.

10.4. *Procedure Visit (Day 0, up to 90 days following Baseline Visit)*

Subjects will have up to 90 days following the Baseline Visit to receive the planned treatment with the Boston Scientific Radiofrequency Ablation System per standard of care. Any reportable adverse events or changes in opioid pain medications will be collected.

- [REDACTED]
- [REDACTED]

Following completion of this visit, subjects may undergo additional radiofrequency ablation procedure(s) as needed, until the 12 month visit window opens, to treat pain targeted during the initial study procedure or new pain not treated as part of the study, with a Boston Scientific Neuromodulation radiofrequency ablation system according to the locally approved Directions for Use, and [REDACTED]

10.5. 1-Month Visit (30 ± 14 days)

During the 1-Month Visit, subjects will return to the clinic for study evaluations. Any reportable adverse events or changes in opioid pain medications since the last study visit will be collected. [REDACTED]

- [REDACTED]
- [REDACTED]
- [REDACTED]
- [REDACTED]
- [REDACTED]
- [REDACTED]
- [REDACTED]
- [REDACTED]
- [REDACTED]
- [REDACTED]
- [REDACTED]

10.6. 3- (90 ± 14 days) and 6-Month (180 ± 30 days) Visits

During the 3- and 6-Month Visits, subjects will return to the clinic for study evaluations. The same assessments performed at the 1-Month Follow-up Visit will be conducted, as outlined in Table 10.1-1.

10.7. 12-Month Visit (365 ± 60 days, End of Study)

During the 12-Month Visit, subjects will return to the clinic for study evaluations. Any reportable adverse events or changes in opioid pain medications since the last study visit will be collected. The same assessments performed at the 1-Month Follow-up Visit will be collected, as outlined in Table 10.1-1.

A subject's participation in the study ends after completion of the 12-Month Visit.

10.8. *Additional RF Procedure (s)*

Subjects may have additional radiofrequency (RF) ablation procedures per standard of care, with commercially approved Boston Scientific Neuromodulation RF ablation systems. Radiofrequency ablation may be repeated to retreat pain targeted during the initial study procedure or may be performed to treat new pain not initially treated as part of the study. Subjects may have as many additional RF procedures as needed, until the 12 month visit window opens, to treat pain during participation in the study. Subjects who decline an additional RF procedure recommended by the study physician will be withdrawn from the study.

Once the need for an additional RF procedure is determined, the procedure should be scheduled as soon as possible. After each Additional RF Procedure, a Study Visit is required between 1 to 3 months (30 – 90 + 14 days) for evaluation and assessment as described in **Table 10.1-1**.

If this time period falls within the visit window of the next Study Visit, these Study Visit assessments will be used. If this is not the case, an additional (Unscheduled) visit is required.

For an Additional RF Procedure, subjects will return to the clinic to first complete pre-procedure assessments and then have the additional RF procedure. Any reportable adverse events or changes in opioid pain medications since the last study visit will also be collected.

| | |
|------------|------------|
| [REDACTED] | |
| ■ | [REDACTED] |
| ■ | [REDACTED] |
| ■ | [REDACTED] |
| ■ | [REDACTED] |
| ■ | [REDACTED] |
| ■ | [REDACTED] |
| ■ | [REDACTED] |
| ■ | [REDACTED] |

Subjects will receive additional RF treatment with a Boston Scientific Neuromodulation Radiofrequency Ablation System per standard of care and according to the local Directions for Use (DFU).

| | |
|------------|------------|
| [REDACTED] | |
| ■ | [REDACTED] |

10.9. *Unscheduled Visits*

Subjects may have as many unscheduled visits as required for device or procedure related visits (e.g. assessing if additional intervention may be warranted) or for evaluation of possible adverse events.

An unscheduled visit is also required to perform follow-up for an additional RF procedure, if there is no Study Visit scheduled 1 to 3 months (30 – 90 + 14 days) after the additional procedure.

10.10. *Study Completion*

All treated subjects will be followed through completion of the 12-Month Visit or study withdrawal as defined in section 9.2.

10.11. *Source Documents*

It is preferable that original source documents are maintained, when available. In lieu of original source documents, certified copies are required to be maintained. A certified copy is a copy (irrespective of the type of media used) of the original record that has been verified (i.e., by a dated signature or by generation through a validated process) to have the same information, including data that describe the context, content, and structure, as the original. Source documentation includes but is not limited to those items noted in Table 10.12-1.

Table 10.11-1: Source Documentation Requirements

| Requirement | Disposition |
|--|---|
| Hospital records and/or clinical and office charts including the evidence of but not limited to inclusion/exclusion criteria, informed consent, exams, procedures and devices used, evaluations, health economic assessments, laboratory results, medications, assessment of adverse events. | Retained at investigational site |
| Assessments and questionnaires | Retained at investigational site and/or electronic data collection platform/EDC |
| Imaging films/prints documenting treatment location | Retained at investigational site |

11. Statistical Considerations

11.1. *Clinical Endpoints*

A number of clinical endpoints are included (but not limited to) in this study, as described below. Continuous variables will be summarized using descriptive statistics which include number of non-missing observations, mean, median, standard deviation, minimum, maximum. For categorical variables, descriptive statistics include frequencies, and percentages of categories. Estimates of all endpoints will be reported, as well as the 95%

confidence intervals. Hypothesis test of change from baseline for the continuous variables may be performed when it is appropriate.

- Proportion of subjects with a 30% or greater reduction from Baseline in targeted pain¹ intensity (*VRS*) at 1-, 3-, 6- and 12-months post-procedure
- Proportion of subjects with a 30% or greater reduction from Baseline in targeted pain¹ intensity (*PPR*) at 1-, 3-, 6- and 12-months post-procedure
- Change in targeted pain¹ intensity from Baseline Visit through 1-, 3-, 6- and 12-months post-procedure (*VRS*)
- Percent Pain Relief in targeted pain¹ through 1-, 3-, 6- and 12-months post-procedure (*PPR*)
- Patient global impression of change at 1-, 3-, 6- and 12-months post-procedure (*PGI-C*)
- Change in disability from Baseline Visit to 1-, 3-, 6- and 12-months post-procedure (*ODIv2.1a*)
- Change in opioid pain medications from Baseline Visit to 1-, 3-, 6- and 12-months post-procedure (Concomitant Medications)

¹Targeted pain – Pain intended to be treated using RF

Additional endpoints will be evaluated post-hoc for data collected in assessments not listed in the predefined clinical endpoints.

11.1.1. Primary Endpoint

11.1.1.1. Hypotheses

No primary endpoint was defined in the study.

11.1.1.2. Sample Size

No sample size calculation was performed.

11.1.1.3. Statistical Methods

No formal statistical hypothesis is planned. Descriptive statistics will be utilized to report the clinical endpoints and their changes from Baseline at 1-, 3-, 6- and 12-months post-procedure.

[REDACTED]
[REDACTED]
[REDACTED]
[REDACTED] who receive treatment with the study device, with no major protocol deviations.

11.2.2. Control of Systematic Error/Bias

Selection of patients will be made from the Investigator's usual patient population. All patients meeting the inclusion/exclusion criteria and having signed the Informed Consent Form will be eligible for participation in the study. The reasons for exclusion, for subjects who sign an informed consent form but do not have an RFA procedure, will be indicated in EDC. Boston Scientific will report to the ethic committee any evidence of fraud, including deliberate tampering with the selection of subjects.

11.2.4. Data Analyses

All statistical analyses will be done using the SAS System software, version 8.2 or later (Copyright © 2000 SAS Institute Inc., [name], USA. All rights reserved). Additional details on these analyses can be found in the Statistical Analysis Plan.

11.2.5. Interim Analyses

No formal interim analyses are planned for the purpose of stopping this study early for declaring effectiveness or futility.

11.2.6. Subgroup Analyses

Subgroup analyses will be performed as appropriate, for example, treatment indication, age, gender, et al.

11.2.8. Multivariable Analyses

No formal covariate analyses are planned.

11.2.9. Changes to Planned Analyses

Any changes to the planned statistical analyses made prior to performing the analyses will be documented in an amended protocol approved prior to performing the analyses. Changes from the planned statistical methods after performing the analyses will be documented in the clinical study report along with a reason for the deviation.

12. Data Management

12.1. Data Collection, Processing, and Review

Subject data will be recorded in a limited access secure electronic data capture (EDC) system.

The clinical database will reside on a production server hosted by Medidata EDC System. All changes made to the clinical data will be captured in an electronic audit trail and available for review by the sponsor or its representative. The associated Rave software and database have been designed to meet regulatory compliance for deployment as part of a validated system compliant with laws and regulations applicable to the conduct of clinical studies pertaining to the use of electronic records and signatures. Database backups are performed regularly.

The Investigator provides his/her electronic signature on the appropriate electronic case report forms (eCRFs) in compliance with local regulations. A written signature on printouts of the eCRFs must also be provided if required by local regulation. Changes to data previously submitted to the sponsor require a new electronic signature by the Investigator acknowledging and approving the changes.

Visual and/or electronic data review will be performed to identify possible data discrepancies. Manual and/or automatic queries will be created in the Medidata EDC system and will be issued to the site for appropriate response. Site staff will be responsible for resolving all queries in the database.

12.1.1. Electronic Questionnaires

Questionnaires in electronic form may be collected directly using an electronic data collection platform at the clinical site (e.g. iPad). After completion by the subject or a clinician, data from the electronic questionnaires are transmitted directly into the EDC system.

12.2. Study Assessments

12.2.1. Adverse Events

Adverse event evaluation will be conducted to identify adverse events occurring during the study and classify them in regard to seriousness, relationship to the procedure and/or device, action taken and outcome. Safety events will be reported as specified in Table 17.4-1.

All device and procedure related non-serious adverse events, all serious adverse events regardless of relatedness, and unanticipated adverse events will be collected from the time of consent through the end of the study.

12.2.2. Beck Depression Inventory (BDI-II)

BDI-II measures the intensity, severity, and depth of depression. It includes a long form of 21 questions, each evaluating a specific depression symptom (e.g., sadness, pessimism, irritability, loss of energy, concentration difficulty, indecisiveness, changes in sleep pattern, fatigue, etc.).

12.2.3. Concomitant Medications

Opioid medications for pain management will be collected throughout the study in order to obtain a full record of medication-related resource utilization. Information will include medication name, dates of prescription, indication or purpose, dose, frequency, and route of administration.

12.2.4. Demography

Demographic information will include date of birth and gender, if allowed/requested by local regulations.

12.2.5. EQ-5D 5 Level (EQ-5D-5L)

EQ-5D-5L is a standardized measure of health status developed by the EuroQol Group in order to provide a simple, generic measure of health for clinical and economic appraisal. Applicable to a wide range of health conditions and treatments, it provides a simple descriptive profile and a single index value for health status that can be used in the clinical and economic evaluation of health care as well as in population health surveys.

EQ-5D-5L is comprised of a descriptive system and a visual analog scale. The descriptive system measures quality of life along five dimensions, including mobility, self-care, usual activities, pain/discomfort, and anxiety/depression, with five levels for each dimension from which subjects are asked to select one. The visual analog scale is used to record the subject's self-rated health on a 20cm vertical line with endpoints labeled 'the best health you can imagine' and 'the worst health you can imagine'.

12.2.6. Medical History

Medical history will include medical and procedural history relating to pain management, onset of chronic pain, all pain-related diagnoses and medical/psychological conditions, medication use etc.

12.2.7. Oswestry Disability Index Version 2.1a (ODI v2.1a)

ODI v2.1a assesses the degree of subject disability due to pain, measuring the impact of pain on activities of daily living. ODI v2.1a is composed of 10 questions that describe the pain and its impact on daily life on a 0 - 5 scale, with higher values indicating the more severe impact.

12.2.8. Pain Intensity (NRS)

Pain Intensity (NRS) is a questionnaire that numerically assesses the intensity of the subject's pain intensities, including overall pain and pain in targeted area(s).

Pain intensity is expressed on a 0 – 10 numeric rating scale (NRS), where 0 indicates “no pain” and 10 indicates “pain as bad as you can imagine”, as reported by the subject.

12.2.9. Pain Intensity (VRS)

Pain Intensity (VRS) is a questionnaire that verbally assesses the intensity of the subject's pain intensities, including overall pain and pain in targeted area(s). This is done based on a clinician interview (e.g. study physician) with the subject.

Pain intensity is expressed on a 0 – 10 verbal rating scale (VRS), where 0 indicates “no pain” and 10 indicates “pain as bad as you can imagine”, verbally reported by the subject to study personnel.

12.2.10. Procedure Information

General information will be collected regarding the radiofrequency ablation procedures performed during the study, including initial and any repeat procedures.

12.2.11. Patient Global Impression of Change (PGI-C)

PGI-C is a seven-point scale that requires the subject to assess how much their condition has improved or worsened relative to their baseline. Subjects will rate themselves as: very much improved; much improved; minimally improved; no change; minimally worse; much worse; or very much worse.

12.2.12. Pittsburgh Sleep Quality Index (PSQI)

PSQI is a self-rated questionnaire assessing sleep quality and disturbances. This questionnaire include 19 individual items grouped into 7 component scores: subjective sleep quality, sleep latency, sleep duration, habitual sleep efficiency, sleep disturbances, use of sleeping medication, and daytime dysfunction. The sum of these 7 scores yields a single global score.

12.2.13. Percent Pain Relief (PPR)

PPR is a questionnaire assessing how much of the subject's overall, low back pain and leg pain has been relieved by the RFA treatment. Pain relief is expressed as a percentage from 0 – 100%.

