6.3. Clinical Endpoints

The following endpoints will be evaluated. Assessments required for deriving each endpoint are denoted in parentheses.

- Proportion of subjects with a 30% or greater reduction from Baseline in targeted pain¹ intensity (*VRS*) at 1-, 3-, 6- and 12-months post-procedure
- Proportion of subjects with a 30% or greater reduction from Baseline in targeted pain¹ intensity (*PPR*) at 1-, 3-, 6- and 12-months post-procedure
- Change in targeted pain¹ intensity from Baseline Visit through 1-, 3-, 6- and 12-months post-procedure (*VRS*)
- Percent Pain Relief in targeted pain¹ through 1-, 3-, 6- and 12-months post-procedure (*PPR*)
- Patient global impression of change at 1-, 3-, 6- and 12-months post-procedure (*PGI-C*)
- Change in disability from Baseline Visit to 1-, 3-, 6- and 12-months post-procedure (*ODIv2.1a*)
- Change in opioid pain medications from Baseline Visit to 1-, 3-, 6- and 12-months post-procedure (Concomitant Medications)

¹Targeted pain – Pain intended to be treated using RF

Additional endpoints will be evaluated post-hoc for data collected in assessments not listed in the predefined clinical endpoints.

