8.2. Inclusion Criteria

Subjects who meet all of the following criteria (see Table 8.2-1) may be given consideration for inclusion in this clinical investigation, provided no exclusion criterion (see Table 8.3-1) is met.

Table 8.2-1: Inclusion Criteria

| | |
|-----------------------------|---|
| Clinical Inclusion Criteria | 
IC1. Study candidate is scheduled to be treated with a commercially approved Boston Scientific RF system for pain per local Directions for Use (DFU)
 
IC2. Signed a valid, IRB/EC/REB-approved informed consent form
 |
|-----------------------------|---|

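### As section 12.2.13 describes it, PPR has no targeted-pain item, so the two PPR endpoints cannot be derived for subjects whose target is clearly neither low back nor leg

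*Combined protocol and SAP*

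**What the plan says.** Section 6.3 lists seven clinical endpoints, repeated in section 11.1 and in the synopsis. Two are derived from PPR:

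- the proportion of subjects with at least a 30% reduction "in targeted pain¹ intensity (*PPR*) at 1-, 3-, 6- and 12-months post-procedure";
- "Percent Pain Relief in targeted pain" at the same four visits.

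The footnote to both defines targeted pain as "Pain intended to be treated using RF". It names no body site.

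Section 12.2.13 says that PPR asks about relief of overall pain and how far "low back pain and leg pain has been relieved by the RFA treatment", on a scale from 0 to 100%. It mentions no item for the targeted area. Section 12.2.8 describes the NRS as "including overall pain and pain in targeted area(s", and section 12.2.9 describes the VRS in the same way.

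The first inclusion criterion (section 8.2) admits anyone "scheduled to be treated with a commercially approved Boston Scientific RF system for pain per local Directions for Use". The exclusion criteria in section 8.3 add no restriction by site. Section 11.2.6 gives treatment indication as an example of a subgroup. Section 11.1 promises an estimate and a 95% confidence interval for every endpoint.

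**The concern.** The endpoint is defined by whatever pain the procedure was meant to treat. The instrument, as described, is defined by fixed body regions. The two coincide only when the target is the low back or the leg.

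For any other target the analyst has two choices, and the readable text decides between them nowhere. One is to leave the PPR endpoints missing, which shrinks the denominator and limits the result to back and leg subjects. The other is to use overall relief, which also reflects pain that the procedure did not address. A comparison by treatment indication would then confound the site of pain with the questionnaire item used to score it.

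Timing also matters. Relief that was not asked about at a visit cannot be recovered reliably later.

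**Working it through.** The plan gives no figure to reproduce: it has no sample size calculation (section 11.1.1.2) and states no mix of treatment sites. The check is to set the sections side by side.

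**1. Endpoint against instrument**

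| Source | Pain covered |
|---|---|
| PPR endpoints (6.3, 11.1) | Targeted pain, any site |
| PPR items (12.2.13) | Overall; low back; leg |
| NRS items (12.2.8) | Overall; targeted area(s) |
| VRS items (12.2.9) | Overall; targeted area(s) |

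Among the three pain instruments, the omission is specific to PPR.

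**2. Who is affected**

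Section 4.2 names cervical, lumbar, sacroiliac, hip and knee joints among the uses of RF in the literature, and section 8.2 excludes none of them.

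- Lumbar: the low back item plausibly applies.
- Sacroiliac, hip, knee: whether these count as low back or leg is not stated.
- Cervical: neither regional item applies. This is the clear case.

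Even for back and leg subjects, no readable rule says which item is the targeted one.

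**3. What is lost**

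For an affected subject: 2 endpoints × 4 visits = 8 values.

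**4. Effect on the estimate**

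Let p be the share of subjects with no matching item. Let R_B be the responder proportion for targeted pain among the other subjects. Among the affected subjects, let R_T be the responder proportion for targeted pain and R_O that for overall pain.

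- Endpoint as defined: (1 − p)R_B + pR_T.
- Affected subjects left out: R_B, which differs from the endpoint by R_B − (1 − p)R_B − pR_T = p(R_B − R_T).
- Overall PPR substituted: (1 − p)R_B + pR_O, which differs by p(R_O − R_T).

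Mean percent relief follows the same algebra, with means in place of proportions. The documents give none of p, R_B, R_T or R_O, so neither the size nor the direction of the difference can be calculated. Leaving subjects out does give a clean estimate of a narrower quantity, if it is labelled as such. Substitution gives a mixture of two quantities.

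**5. Redaction**

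The conflicting sections are all unredacted, so blacked-out text does not create the conflict. It could hide its resolution, as discussed under the objection.

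**The case against.** The strongest reply is that section 12.2.13 is a two-sentence summary and not the form. The questionnaire is not reproduced, the assessment lists for the visits are blacked out, and Table 10.1-1 is not shown. Section 11.2.4 refers to a Statistical Analysis Plan for further detail, so a mapping rule may exist there. The synopsis and sections 6.3 and 11.1 all name PPR as the source for targeted pain. Loose wording in 12.2.13 is therefore as consistent with the documents as a defective form. This stands, and it limits the claim to the instrument as described. It does not remove the need to act, because either the description or the form has to change.

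It is also fair that the harm is contained. No primary endpoint is defined (section 11.1.1.1), no formal hypothesis is planned (section 11.1.1.3), and each PPR endpoint has a VRS counterpart with a targeted-area item.

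A reader might also infer that, because "Pain relief is expressed as a percentage from" 0 to 100%, subjects who worsen are scored 0 and mean PPR is biased upward. The documents do not support this. Zero is the valid score for pain that has not been relieved, and nothing says that PPR is meant to estimate net percent change. A worsened subject is a non-responder at the 30% threshold either way. Worsening is captured by VRS change, by three PGI-C categories (section 12.2.11) and by adverse event reporting (section 17.2, notes 3 and 4).

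**Conclusion.** The inconsistency holds for the instrument as section 12.2.13 describes it. The described items cannot yield the two PPR endpoints for subjects whose target is clearly neither low back nor leg, and overall relief is not an equivalent measure. The reach is two of seven clinical endpoints, at four visits each.

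Three stronger readings go beyond the text:

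- That the form in use lacks a targeted-area item. The form is not shown.
- That every sacroiliac, hip and knee subject is affected. The documents do not say how those sites map to the items.
- That a percentage of subjects can be given. Section 4.2 reviews RF in general and says nothing about this study's case mix.

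The point should be fixed, but it does not threaten the study. Reporting is descriptive, and the VRS endpoints can describe targeted pain at every site.

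**What to change.** 1. Check the PPR form in use against section 12.2.13.
2. If the form has a targeted-area item, correct 12.2.13 to say so. No data are lost.
3. If it does not, change PPR to ask about overall pain and the targeted area(s) recorded before the initial procedure, as for VRS and NRS. The time anchor is needed because sections 10.4 and 10.8 allow later RF procedures for new pain, and the definition of targeted pain has no date attached.
4. For visits already completed without the item, analyse the two PPR endpoints only where the recorded target matches a low back or leg item. State in the SAP which item counts for which target, including sacroiliac, hip and knee. Do not substitute overall PPR. Report the reduced denominator at each visit and label the result as covering low back and leg targets only.

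The cost is a protocol amendment, which section 14.3 makes subject to IRB/EC/REB review and approval before it takes effect, in a multi-center global study. A form change also needs an eCRF update and leaves a smaller PPR denominator for earlier subjects. If follow-up is already complete, which the documents do not show, a missing item can no longer be added and only step 4 applies.
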